4.4 Study Exit Data Elements

The following data will be recorded when the patient exits the study:

- 1. Study day of exit from study (1 to 14)
- 2. Time of exit from study (hh:mm)
- 3. Reason for exiting study:
 - (a) Reached end of study day 14
 - (b) Opioid therapy was discontinued
 - (c) Patient died
 - (d) Patient discharged from PICU
- 4. If reason for study exit was PICU discharge:
 - (a) Was patient on lorazepam at the time of PICU discharge? (Yes or No)
 - (b) Was patient on methadone at the time of PICU discharge? (Yes or No)
 - (c) Was patient on buprenorphine at the time of PICU discharge (Yes or No)
 - (d) Was patient on clonidine (for prevention or treatment of opioid withdrawal) at the time of PICU discharge (Yes or No)

5 Data Analysis

5.1 Analysis of Primary Endpoint

The primary endpoint for the MOTIF Study is the incidence of opioid tolerance among PICU patients receiving morphine or fentanyl infusions for analgesia and sedation. For the purposes of this study, opioid tolerance is defined by a doubling of the total daily opioid dose from the initiation of opioid therapy (0-24 hours) in the PICU. Tolerance can develop at any time during opioid therapy; therefore, as would be the case for an intention-to-treat analysis in a clinical trial, subjects who die or are discharged from the PICU will be included in the denominator for this endpoint, irrespective of number of days in PICU prior to death or discharge. We will examine the incidence of this endpoint 7 days and 14 days after initiation of morphine or fentanyl infusion therapy, in order to help determine appropriate parameters for future clinical trials. Rates of the primary endpoint will be summarized as proportions achieving tolerance by 7 days and by 14 days after opioid therapy initiation, together with appropriate confidence intervals.

5.2 Analysis of Secondary Endpoints

Secondary endpoints for the MOTIF study are:

- 1. Average daily fentanyl or morphine dose within age groups (μ g/kg/day, all opioid drugs will be normalized to fentanyl equivalent doses using well-established opioid conversion ratios);
- 2. Peak fentanyl or morphine infusion rate (μ g/kg/hour, again all opioid drugs will be normalized to fentanyl equivalent doses using published opioid conversion ratios);
- 3. Total cumulative dose (mg/kg) and duration of fentanyl or morphine exposure (hours) during the stay, measured from the time of the first dose given after PICU admission and until study exit.

We will examine alternative definitions of tolerance, which may become possible secondary outcomes in future trials. We will describe these continuous secondary outcomes graphically, as well as using measures appropriate to their distributions, including mean and standard deviations for data approximating a normal distribution, and medians and interquartile ranges for substantially skewed outcomes.

As for the binary primary endpoint, we will report summary statistics of these secondary endpoints according to key study variables, and perform exploratory between-subgroup comparisons. Here, t-test/ANOVA or their nonparametric analogues will be used to assess relationships between categorical and categorized factors, while correlations and scatterplots will provide further information on associations with continuous factors. Multivariable analyses to assess factors independently predictive of secondary outcomes will be performed using linear regression models when possible (if goodness-of-fit criteria such as assessment of residual distributions indicates a satisfactory model). For excessively skewed outcomes, transformation may facilitate use of the linear regression model.

5.3 Explanatory Variables and Additional Analyses

These include demographic and clinical variables (such as age, gender, history of prior exposure, age at first exposure, duration of opioid therapy, use of concomitant medications, etc.) in order to identify possible risk factors for development of opioid tolerance during PICU therapy, and to generate hypotheses for future studies. In addition, since some opioid drugs are highly lipophilic (e.g. fentanyl) and others are not (e.g. morphine), we will calculate BMI and ideal body weight to evaluate the impact of increasing obesity on opioid tolerance.

In exploratory analyses, we will also assess rates of the primary and secondary endpoints according to other explanatory study variables. Factors examined in these analyses will include age, gender, history of prior exposure, age at first exposure, duration of opioid therapy, use of concomitant medications, and BMI. For continuous factors, categories will be defined using clinically appropriate cut-points, or quartiles of the observed data when such cut-points do not exist or are equivocal. Chi-squared tests or exact analogues will be used to compare proportions achieving the endpoint between subgroups. Logistic regression models will be used to assess factors that are independently predictive of tolerance, starting with candidate factors showing at least a weak statistical trend toward unadjusted association with the endpoint.

This study will be collecting information on other outcomes, for example, clinical status at PICU discharge and other clinical variables. The general strategy for analyses of other outcomes collected in this study will follow that specified for the primary and secondary study endpoints. Other binary or categorical outcomes such as PICU and hospital survival will be compared using chi-square tests or exact analogues. For other continuous outcome variables, summary statistics and box-plots will be used to investigate their distributions. Where indicated in order to ensure satisfaction of assumptions, we will either use transformations or non-parametric statistics.

Univariate and multivariable regression analyses as described above (logistic for binary outcome, and linear regression for continuous outcomes appropriately transformed when necessary) will be used to assess the effects of covariates such as age, gender, and race. Tolerance-related parameters, such as time to doubling of the opioid dose, may be used as predictors in selected analyses. For outcomes recorded as integral days, such as time in PICU, we will also examine Poisson regression analyses using the SAS GENMOD procedure.

Exploratory repeated measures analyses will make use of the daily data elements collected in this study to assess patterns of opioid dosing across time, and examine factors associated with differences in such patterns. The general linear mixed model will be used for these analyses, to control for within-subject correlation of observations across time, and to appropriately model trajectories. Polynomial or spline models may be used as appropriate in these exploratory analyses to allow maximum flexibility in modeling observed patterns of dosing or response across time.

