3.6.2 Exclusion Criteria

Children are ineligible to be enrolled as study subjects if ANY of the following is true or anticipated:

- are premature and have not reached the post-conceptional age of 37 weeks, OR
- have a history of drug abuse or alcohol dependence, OR
- for patients less than 3 months old, if the mother has a history of drug abuse during this pregnancy, OR
- are on ECMO or are likely to be placed on ECMO support within 24 hours after PICU admission, OR
- are receiving continuous infusions (of any drugs) for nerve blocks, plexus blocks, or epidural anesthesia, OR
- are receiving opioid therapy via patient-controlled analgesia (PCA) pumps, OR
- were receiving regularly scheduled opioid therapy for more than one week before admission to the PICU, OR
- previously enrolled in this study, OR
- lack of commitment to aggressive intensive care therapies.

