3.7 Inclusion of Women and Minorities

The gender, ethnic and racial composition of patients enrolled in all CPC-CRN studies is a function of the characteristics of patient populations at each Clinical Center selected by the National Institute for Child Health and Human Development (NICHD) to participate in the network. During this study, the Data Coordinating Center (DCC) will monitor patient accrual by race, ethnicity, and gender. If necessary, additional recruitment efforts will be made at specific centers to ensure that the aggregate patient sample contains appropriate gender and minority subsets.

4 Data Management

Research data will be collected at the time of enrollment and daily data collection will continue until the last dose of opioids, or a total of 14 days after enrollment, or the patient's death or PICU discharge, whichever occurs first.

This protocol includes a detailed list of data elements to be collected, and if data elements are added or subtracted from this, a protocol amendment will be produced. However, specific choice sets for these data may be amended without being considered a change to this protocol. The choice sets that are listed in the protocol are intended to help the reader completely understand the intent of the data element and to assist implementation of the electronic data collection system by the CPCCRN DCC.

Data will be entered into an electronic data collection system to be designed and implemented by the CPCCRN DCC. The Study Coordinator may choose to print hard copy forms to use as worksheets. If used, the paper worksheets should be retained at the clinical center in a locked file cabinet within a locked office until the study is complete and all CPCCRN publications associated with MOTIF have been accomplished.

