4.2 Study Entry and Day One Data Elements

The following data elements will be obtained and recorded when a patient is enrolled into the study:

- 1. Study Code ID
- 2. Clinical Center ID
- 3. Date of Enrollment
- 4. Date and Time of Admission to PICU
- 5. Gender
- 6. Race
 - American Indian or Alaska Native A person having origins in any of the original peoples of North and South America, including Central America, and who maintains tribal affiliation or community attachment.
 - Asian A person having origins in any of the original peoples of the Far East, Southeast Asia, or the Indian subcontinent, including, for example, Cambodia, China, India, Japan, Korea, Malaysia, Pakistan, the Philippine Islands, Thailand, and Vietnam.
 - **Black or African American** A person having origins in any of the black racial groups of Africa.
 - Native Hawaiian or Other Pacific Islander A person having origins in any of the original peoples of Hawaii, Guam, Samoa, or other Pacific Islands.
 - White A person having origins in any of the original peoples of Europe, the Middle East, or North Africa.
 - Other (provide text) Should provide text description.

Stated as Unknown Explicitly stated as unknown.

- 7. Ethnicity
 - Hispanic or Latino
 - Not Hispanic or Latino
 - Stated as Unknown
- 8. Date of Birth
- 9. Height (cm)
- 10. Weight (kg)

- 11. Admission Pediatric Risk of Mortality III (PRISM III) Score (Based on first 12 hours of PICU admission)
- 12. History of previous PICU admission (Yes or No)?
- 13. History of NICU admission (Yes or No)? If yes, duration in days.
- 14. History of surgical operation in previous hospitalizations (Yes or No)?
- 15. Primary Diagnostic Category (Select One)
 - Asthma (reactive airway disease)
 - Cancer
 - Cardiac arrest w/in 24 hours (closed chest massage)
 - Chromosomal abnormality
 - Diabetes
 - Drug overdose (e.g. ingestion, toxicity)
 - Gastroesophageal reflux
 - Cardiovascular disease acquired
 - Cardiovascular disease congenital
 - HIV infection
 - Hypoxic-ischemic encephalopathy of recent onset (acute, not static)
 - Medical device malfunction
 - Meningitis
 - Pneumonia / bronchiolitis
 - Seizures (includes complications of seizure therapy)
 - Sepsis
 - Shock
 - Suicide attempt (includes intentional drug overdose)
 - Transplant
 - Trauma
 - Other Diagnosis
- 16. Secondary Diagnostic Category (Select One)
 - Asthma (reactive airway disease)

- \bullet Cancer
- Cardiac arrest w/in 24 hours (closed chest massage)

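### Section 5.3 names outcomes and risk factors that the Section 4 data list does not collect, collects only up to study exit, or captures only by proxy

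*Protocol*

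**What the plan says.** **Planned analyses.** Section 5.3 states: "Factors examined in these analyses will include age, gender, history of prior exposure, age at first exposure, duration of opioid therapy". Concomitant medications and BMI complete the list, which makes seven factors. Sections 1.5 and 3.5 also name "history of prior exposure, age at first exposure". For further outcomes, Section 5.3 says: "Other binary or categorical outcomes such as PICU and hospital survival will be compared", by chi-square or exact tests. It adds: "For outcomes recorded as integral days, such as time in PICU, we will also examine Poisson regression analyses". Clinical status at PICU discharge is given as another outcome on which information will be collected.

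**Data to be collected.** Section 4 presents a detailed list of elements and says that "if data elements are added or subtracted from this, a protocol amendment will be produced". Only the answer options may change without an amendment. Daily collection stops at the earliest of the last opioid dose, 14 days, death or PICU discharge. At exit, Section 4.4 records "Study day of exit from study (1 to 14"), the time, and one of four reasons: end of Day 14, opioids discontinued, death, or PICU discharge. On history, Section 4.2 has "History of previous PICU admission (Yes or No"), NICU admission with its duration, and surgery in earlier hospitalisations.

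**Eligibility.** Section 3.6.2 excludes children who "were receiving regularly scheduled opioid therapy for more than one week before admission to the PICU". A child with up to one week of such therapy may enter.

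**The concern.** An analysis needs a variable, and here the variables are fixed in the protocol. An analysis plan can choose a model, a coding or a rule for missing values, but it cannot create a hospital outcome or a discharge date that no one recorded. If the sites follow Section 4 exactly, some analyses in Section 5.3 cannot be done, and others would use values that mean something different from their names.

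Two things are at stake. Risk factors are one of only two specific aims, and Section 5.4 intends that predictors found here may be used for stratified enrolment in later trials. Prior opioid exposure is an obvious candidate, and it is the one least well measured. For the stay and survival outcomes, the danger is that study exit is silently read as the end of the PICU stay.

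**Working it through.** The protocol gives no figure on this point, so the check sets Section 5.3 against Sections 4.2 to 4.4.

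| Named in 5.3 | Nearest listed element | What can be obtained |
|---|---|---|
| Hospital survival | Death as a reason for study exit (4.4) | Deaths up to study exit only; no hospital discharge or later vital status |
| Time in PICU | PICU admission date and time (4.2, item 4); exit day, time and reason (4.4) | Exact for exits by PICU discharge or death; cut off for the other two reasons |
| PICU survival | Exit reason (4.4) | Known for exits by discharge or death; unknown for the other two |
| Status at PICU discharge | Four drug items, asked only if exit was PICU discharge (4.4, item 4) | Nothing for children who exit by opioid discontinuation or Day 14 |
| History of prior exposure | Previous PICU, NICU and surgical history (4.2, items 12 to 14) | Proxies; none asks about opioids |
| Age at first exposure | Date of birth (item 8); first PICU dose, Time 0 (item 20) | Age at Time 0 of this stay |

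**Direction of the error in time in PICU.**
- For every child, the observable time runs from PICU admission to study exit.
- If exit is PICU discharge or death, observed time = true stay.
- If exit is opioid discontinuation or the end of Day 14, observed time ≤ true stay, because the child may remain in the PICU.
- Treating all observed times as complete can therefore only shorten the stays.
- For opioid-discontinuation exits, the observed time is the interval from admission to Time 0 plus the time from Time 0 to the stopping of opioids. The outcome then largely repeats duration of opioid therapy, which is itself one of the seven factors.
- Day 14 exits are the children still on opioids, so the cut-off also falls on those with the longest exposure.

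**Direction of the error in PICU survival.** If exits by opioid discontinuation or Day 14 are counted as survivors, any later PICU death is missed. Observed deaths ≤ true deaths.

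**Prior exposure.** Up to one week of scheduled opioids before admission is compatible with entry, and Section 3.1 places particular risk at 4 or more days of continuous infusion. Scheduled therapy is not necessarily an infusion. Even so, a child may arrive with several days of opioid exposure that no listed element records.

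**Age at first exposure.** Age and age at Time 0 differ only by the short gap between admission and the first PICU dose. For a child exposed in an earlier admission, the true age at first exposure is not recorded.

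**Count.** Two of the seven named factors are weakened.

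**Primary endpoint.** It needs only the daily opioid doses, so its precision is not affected by these gaps. With N = 450, 1.96 × √(0.25 × 0.75 / 450) = 0.040 at a 25% rate and 1.96 × √(0.50 × 0.50 / 450) = 0.046 at 50%. Both agree with the 4 to 5% in Section 5.4.

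**The case against.** The best defence has three parts.

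*The variables are not absent.* Nowhere does the protocol define prior exposure as measured opioid dosing. The PICU, NICU and surgical items may well be what was meant. Age at first exposure can be computed for this stay, and PICU stay is exact for exits by discharge or death. This stands. A reader might infer that two of the seven factors cannot be analysed at all, or that no PICU discharge date exists for anyone; the documents do not support either. Study-exit cut-off also does not touch the two baseline factors. What remains is that the proxies are not opioid-specific and that the derived age adds almost nothing to age.

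*The analyses are minor.* Hospital survival and time in PICU appear as examples under other outcomes, and the factor analyses are called exploratory. This also stands and limits the weight of the point. It does not remove the mismatch, because Section 5.3 says that these analyses will be made and Section 4 closes the list.

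*The choice of model can wait.* A reader might go on to fault Poisson regression for lengths of stay. That is not supported. It is offered in addition to other methods, Section 5.3 provides for transformations and non-parametric statistics, and handling of dispersion is a matter for an analysis plan. Missing data elements are not.

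**Conclusion.** The point holds as an internal inconsistency between Sections 4 and 5.3. Hospital survival cannot be obtained. Time in PICU, PICU survival and status at PICU discharge are incomplete for every child who exits by opioid discontinuation or at Day 14, and stays would be understated if exit were taken as the end of stay. Prior exposure is available only through non-opioid proxies, and age at first exposure only as a near copy of age.

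The number of children affected cannot be given, because the protocol does not project exits by reason or the share with earlier opioid use. The conclusion assumes only that sites collect what Section 4 lists and nothing more.

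A reader might infer that unrecorded earlier opioids raise the baseline dose, hide later doubling and so undermine the primary endpoint. The documents give no evidence or size for this. The endpoint is defined against the first 24 hours of opioid therapy in the PICU and can be calculated as defined. The damage is to Specific Aim 2 and the other outcomes. The change should be made, but the main incidence estimate does not depend on it.

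**What to change.** Either collect the data or narrow the analyses.

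1. **Collect.** Add to Section 4.2: any opioid exposure in the week before PICU admission (Yes/No, number of days), and any earlier opioid exposure (Yes/No, with age at first exposure if known). Add to Section 4.4, for all subjects whatever the exit reason: PICU discharge date, and vital status at PICU and at hospital discharge.
2. **Or narrow.** Delete hospital survival and time in PICU from Section 5.3, and limit any statement on PICU survival or status at PICU discharge to what is observed by study exit. In Sections 1.5, 3.5 and 5.3, redefine prior exposure as previous PICU admission, NICU admission and surgery, and drop age at first exposure.

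The first option costs a few chart fields per child, a return to the chart after study exit, and an amendment that each site's review board must see. Part of the work is already done, since sites must look at opioid use before admission to apply the exclusion but do not store the answer. The second option adds no data collection but gives up the named outcomes and a sharper test of one risk factor.

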4.3 Subsequent Daily Data Elements

Study Day One is the day of enrollment, beginning at the time of the first morphine or fentanyl administration in the PICU, and ending at 23:59 on that day. Each subsequent study day is defined as midnight (00:00) to 23:59. On each subsequent day (not study day one), the following data elements

Sedative Drugs and Components Sedative Drugs Answer Ketamine Yes or No Propofol Yes or No Chloral hydrate Yes or No Chlorpheniramine Yes or No Clonazepam Yes or No Diazepam Yes or No Droperidol Yes or No Etomidate Yes or No Yes or No Haloperidol Yes or No Hydroxyzine Methohexital Yes or No Yes or No Pentobarbital Phenobarbital Yes or No Promethazine Yes or No Yes or No Thiopental Yes or No Other (specify)

Table 1: Sedative agents.

Analgesic Drugs and	Components
Analgesic Drugs	Answer
Dexmedetomidine	Yes or No
Acetaminophen	Yes or No
Ibuprofen	Yes or No
Acetylsalicylic acid	Yes or No
Alfentanil	Yes or No
Buprenorphine	Yes or No
Butorphanol	Yes or No
Clonidine	Yes or No
Codeine	Yes or No
Dextromethorphan	Yes or No
Hydromorphone	Yes or No
Ketorolac	Yes or No
Meperidine	Yes or No
Methadone	Yes or No
Nalbuphine	Yes or No
Oxymorphone	Yes or No
Remifentanil	Yes or No
Tramadol	Yes or No
Other (specify)	Yes or No

Analgesic Drugs and Components

Table 2: Analgesic agents.

will be collected. This daily data collection will continue through Study Day 14, discontinuation of opioid therapy, death, or PICU discharge, whichever occurs earliest.

- 1. Date of data collection
- 2. Study day number (2 to 14)
- 3. Weight (kg) last measured or estimated weight
- 4. Was morphine or fentanyl infusion weaned (decreased) in the past 24 hours? (Yes or No)
- Was morphine or fentanyl infusion discontinued in the past 24 hours? (Yes or No) If yes to this question,
 - (a) Was morphine or fentanyl infusion restarted in the past 24 hours? (Yes or No)
 - (b) Were intermittent opioid doses started in the past 24 hours? (Yes or No)
- 6. Were muscle relaxants used in the past 24 hours? (Yes or No)
- 7. Were physical restraints used in the past 24 hours? (Yes or No)
- 8. Did inadvertent or unplanned dislodgement of an endotracheal tube occur in the past 24 hours? (Yes or No)
- 9. Did inadvertent or unplanned dislodgement of a central venous line occur in the past 24 hours? (Yes or No)
- 10. Did inadvertent or unplanned dislodgement of an arterial line occur in the past 24 hours? (Yes or No)

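### BMI is tested against three opioid-dose endpoints that are themselves divided by weight, so an inverse association can arise by arithmetic unless dose rises in full proportion to actual weight

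*Protocol*

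**What the plan says.** Protocol section 5.2 lists the secondary endpoints:

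- "Average daily fentanyl or morphine dose within age groups", in micrograms per kg per day;
- "Peak fentanyl or morphine infusion rate", in micrograms per kg per hour;
- "Total cumulative dose (mg/kg) and duration of fentanyl or morphine exposure (hours) during the stay".

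Section 4.3 (items 15 and 16) has the daily total and the peak hourly dose recorded already divided by weight. The weight collected each day (item 3) is the "last measured or estimated weight".

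Section 5.3 then states that "we will also assess rates of the primary and secondary endpoints according to other explanatory study variables". The factor list ends with "age at first exposure, duration of opioid therapy, use of concomitant medications, and BMI". For continuous factors, section 5.2 says that "correlations and scatterplots will provide further information on associations with continuous factors". It also provides for t-tests or ANOVA over categories and for linear regression.

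Ideal body weight appears once in the analysis sections: "we will calculate BMI and ideal body weight to evaluate the impact of increasing obesity on opioid tolerance". It is not named as a divisor for any dose endpoint, and no analysis of absolute dose is described.

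**The concern.** BMI is weight over height squared, and each of the three dose endpoints is dose over weight. Correlating them puts weight on both sides with opposite signs. Suppose two children of the same height receive the same absolute dose and one is heavier. The heavier child has the higher BMI and the lower dose per kg, with no difference in opioid requirement.

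A reader of the resulting correlation, quartile table or regression could conclude that obese children need less opioid when only the divisor has moved. The result could also travel beyond this study. Section 5.4 allows factors predictive of secondary outcomes to be used for stratified enrollment in later trials, and section 5.3 says the explanatory work is meant to generate hypotheses. A larger sample or a stricter significance level would not remove an artefact of this kind.

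**Working it through.** **The plan's own figures.** The protocol gives no figure for the BMI analysis. It gives n = 450 and a precision of 4-5% for the tolerance proportion (section 5.4). The 95% half-width is 1.96 × √(p(1-p)/450), which is 4.0% at p = 0.25 and 4.6% at p = 0.50. That agrees with the plan, and this point does not touch it. Only n = 450 is carried forward.

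**Inputs that are not in the protocol (assumptions).**

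- s_b, the SD of log(actual weight / ideal weight): 0.15 to 0.20.
- s_d, the SD between patients of log dose per ideal kg: 0.6 to 0.8.
- k, the share of excess weight that absolute dose does not follow: 1 (dose follows ideal weight), 0.5 or 0 (dose fully proportional to actual weight).

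**One child.** At 140% of ideal weight and with the same absolute dose as at ideal weight, the recorded dose per kg is lower by 1 - 1/1.4 = 29%.

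**The cohort, age fixed.** At a given age, take log BMI to move with b = log(weight/ideal weight). Let e be the rest of log dose, unrelated to b. Then log dose per actual kg = e - k·b, and

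r = -k·s_b / √((k·s_b)² + s_d²).

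The chance of a two-sided p < 0.05 follows from Fisher's z, with mean atanh(|r|) × √447.

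| k | s_b | s_d | r | significant |
|---|---|---|---|---|
| 1 | 0.15 | 0.8 | -0.18 | 98% |
| 1 | 0.15 | 0.6 | -0.24 | >99% |
| 1 | 0.20 | 0.8 | -0.24 | >99% |
| 1 | 0.20 | 0.6 | -0.32 | 100% |
| 0.5 | 0.15 | 0.8 | -0.09 | 51% |
| 0.5 | 0.15 | 0.6 | -0.12 | 75% |
| 0.5 | 0.20 | 0.8 | -0.12 | 75% |
| 0.5 | 0.20 | 0.6 | -0.16 | 94% |
| 0 | any | any | 0 | 5% |

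First row as an example: 0.15 / √(0.0225 + 0.64) = 0.15 / 0.814 = 0.184.

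**Check by simulation** (2,000 studies of 450; s_b = 0.20, s_d = 0.8):

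- k = 1: mean r = -0.24. The top BMI quartile has a geometric mean dose per kg 0.61 times that of the bottom quartile. ANOVA over quartiles is significant in 99% of runs. With dose per ideal kg, 5.2% are significant, which is nominal.
- k = 0.5: 75% are significant per actual kg and 75% per ideal kg, with opposite signs.
- k = 0: 5.9% are significant per actual kg, but 99.9% per ideal kg. The ideal-weight divisor then creates the reverse artefact.

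**Age spread.** The cohort runs from term infants to under 18 years, so BMI also varies with age. If age adds an assumed SD s_a of 0.10-0.15 to log BMI, unrelated to dose per kg, r is multiplied by s_b / √(s_b² + s_a²). The ranges become -0.13 to -0.28 (79-100% significant) for k = 1 and -0.07 to -0.15 (29-88%) for k = 0.5.

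**What is not affected.** Tolerance is a doubling of a child's daily dose relative to the same child's first 24 hours. Dividing both doses by the same weight leaves the ratio unchanged, so only day-to-day changes in recorded weight remain. Duration in hours has no divisor.

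**The case against.** A reader might infer that the protocol's obesity question as a whole is compromised. The documents do not support that. Sections 1.5, 3.5 and 5.3 pose the question for opioid tolerance, and weight essentially cancels in that endpoint.

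A reader might also infer that the bias is certain. It is not: the protocol does not say how prescribed dose relates to weight, and with dosing fully proportional to actual weight the artefact is zero.

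Three further objections have force.

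- The comparisons are labelled exploratory, and BMI is one factor among several. That limits the weight of the point, but section 5.4 lets predictors of secondary outcomes inform later trials, so the label does not dispose of it.
- The choice of divisor and of model covariates often belongs in a statistical analysis plan, and the ingredients (height, weight, ideal body weight) are already planned. However, the protocol itself fixes the per-kg outcomes and pairs them with BMI, so the problem lies in what is written and not in what is left out.
- A lower dose per actual kg in heavier children would be a correct description of what was given. The error would come only from reading it as lower need. That is so, and it is why the fix includes a rule for interpretation.

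**Conclusion.** The point holds in a limited form. For average daily dose, peak rate and cumulative dose, the BMI analyses in section 5.3 can show an inverse association produced by the shared weight term. With age fixed and the assumed SDs above, it is r = -0.18 to -0.32 (98-100% of studies significant) if dose follows ideal weight, and r = -0.09 to -0.16 (51-94%) if half the excess weight is not followed. It is absent if dose follows actual weight fully. Age-related spread in BMI lowers these figures. The sizes rest on two assumed SDs and an assumed dosing pattern, none of them given in the protocol, so they illustrate the risk and do not predict a result. The primary endpoint, duration of exposure, the sample size and the stated precision stand as they are.

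**What to change.** In section 5.3, for BMI analyses of the three per-kg dose endpoints only:

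1. State that the divisor is the recorded weight.
2. Add one of two analyses: (a) dose per kg of ideal body weight, obtained as recorded mg/kg × weight / ideal weight; or (b) a linear model of log absolute dose with log weight and log ideal weight as covariates.
3. Interpret a BMI association as an obesity effect only if it does not depend on the divisor. Replacing one divisor by the other is not enough, because the ideal-weight divisor gives a false positive association when dose follows actual weight. For any dosing pattern between the two extremes, the two divisors give opposite signs.

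The cost is a few sentences and a little more exploratory analysis. Height and weight are already collected and ideal body weight is already to be calculated, so no new data are needed and the sample size does not change.
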